4.1 Inclusion Criteria

1. Willing and able to give informed consent
2. ≥ 18 years of age
3. Symptoms and signs consistent with PCT and well documented biochemical diagnosis (urinary total porphyrin excretion > 500 mcg/g creatinine with HPLC pattern typical of PCT—predominance of 8- and 7-carboxyl porphyrins [$>50\%$ of total])
4. Clinical diagnosis of PCT established by a study PI
5. Chronic hepatitis C: HCV RNA positive and quantifiable in serum detected within 90 days of enrollment, and documented HCV genotype for which Harvoni is an approved therapy: genotype 1, 4, 5, or 6.
6. Women of child-bearing potential must be willing to avoid pregnancy and use an accepted and effective contraceptive method during treatment.

4.2 Exclusion Criteria

1. Women who are pregnant or who are breast-feeding
2. Patients who have already started treatment of PCT with phlebotomy or low dose hydroxychloroquine or chloroquine, or who have been in such treatment in the past 30 days
3. Patients who have already started another treatment regimen for CHC, or who have taken such treatment in the past 30 days
4. HIV infection with CD4 counts at baseline less than 350/ μ L or with evidence of any active AIDS-defining illnesses
5. Ongoing active alcohol abuse, defined as a history of drinking more than 25 drinks of alcohol per week during most weeks in the prior 4 months (History of prior, but not current alcohol abuse will NOT be grounds for exclusion because we seek to treat subjects with PCT and CHC of the type typically seen in clinical practice)
6. Any ongoing active IV drug use
7. Patients who are taking Amiodarone or who have taken Amiodarone within 60 days prior to enrollment
8. Patients who are taking, or within the prior 28 days have taken, rifampicin or St John's wort (*Hypericum perforatum*), both of which are P-gp inducers, which may significantly reduce the drug levels and therapeutic effects of Harvoni
9. Uncontrolled diabetes (Hgb A1c $>9.5\%$ within 60 days prior to enrollment)
10. Chronic hepatitis B
11. Autoimmune hepatic liver injury—autoimmune hepatitis, primary biliary cholangitis/sclerosing cholangitis or overlap syndrome
12. Alcoholic hepatitis

13. Other metabolic disorders of the liver, e.g. Alpha 1 antitrypsin deficiency with ZZ Pi type, Wilson's disease
14. Prior known or suspected drug-induced liver injury within 6 months of enrollment
15. Known or suspected hepatocellular carcinoma
16. On liver transplant list, or current MELD >12
17. History of liver transplant
18. Estimated GFR (creatinine clearance) <30 mL/min (per Sofosbuvir being cleared by the kidney)
19. Serum ALT or AST >10x upper limit of normal
20. Serum bilirubin >2 mg/dL (excluding patients with known or suspected Gilbert's syndrome)
21. Any other comorbid condition, which in the opinion of the investigator precludes participation
22. Incarcerated individuals

4.3 Recruitment of Participants

The methods of recruitment will be:

- A. *Patients followed by any of the Investigators in the Porphyrias Consortium:* Each of the Investigators is a Porphyria specialist in a Porphyria Center, and provides clinical care to individuals suspected of and diagnosed with porphyria, providing diagnostic and follow-up evaluations, consultations, and/or treatment. For such patients who are likely to be eligible for the study, the Investigators will either discuss the study with the patient during a clinical visit or will contact the patient by telephone, email, or mail, as appropriate per Central IRB (CIRB) approval. Any efforts to contact and recruit patients and families will be with CIRB approval and adhere to standards for ethical conduct of research and be fully HIPAA compliant.
- B. *Referrals from the American Porphyria Foundation (APF) to the Porphyrias Consortium centers:* The APF is an advocacy group that provides education about porphyria to patients, their families, healthcare professionals, and the public and supports porphyria research. Their outreach program includes a website, as well as periodic newsletters and special announcements emailed and/or mailed to individuals who have registered with the APF with information about new developments in treatment, porphyria-related education opportunities, and research studies available through the Porphyrias Consortium. Information about research studies includes contact information for the studies if they are interested in obtaining additional information or participating. The focus will be on patients and physicians from the following specialties: gastroenterologists, hepatologists, infectious disease physicians, and dermatologists.
- C. *Non-study Physician referrals:* Physicians providing clinical care to individuals suspected of or diagnosed with PCT who are not investigators in this study may refer patients who may be eligible for and express interest in the study to a Porphyrias Consortium center.

D. **Self-referrals:** Including family members of individuals diagnosed with PCT (proband) and other individuals who may have heard about the study from other subjects or prospective subjects. In the case of family members, initial contact with the family member will not be made by the study team. The proband will be asked to contact such family members, requesting that they contact the study coordinator or to register through the RDCRN-Porphyria Consortium if interested in obtaining additional information or participating.

This study is registered on clinicaltrials.gov (NCT 03118674).

In the case of patients followed by one of the Consortium Investigators, the physician/Investigator or study coordinator will either: (a) contact the patient by telephone, email or mail informing him/her of the study and requesting that he/she contact the study coordinator if interested in obtaining additional information or participating, or; (b) discuss the study in-person during a clinical visit; informed consent may be obtained at this time. In all other cases, prospective subjects are instructed to contact the study coordinator, either the Project Manager or a site-specific study coordinator, by telephone, email or mail if interested in obtaining additional information or participating.

All patients will be encouraged to simultaneously enroll in the Longitudinal Study of the Porphyrias (PC7201), however it will not be required for inclusion into this study.

4.4 Retention Strategies

Only a small number of specialists have the expertise to evaluate and treat individuals with PCT. Clinical relationships established by the investigators with patients who enroll in this study will provide a context for increased communication with patients and their primary physicians that can facilitate retention. Furthermore, this study will provide a number of beneficial services to the participants and their primary physicians that will enhance retention. These include providing Harvoni, periodic evaluations, repeat laboratory testing, and information on new research developments in the field. Coordinators and other personnel at each site will also work to maintain close contact with participants, including regular clinic visits, newsletters and communication by phone, email and web sites. Counseling services will be provided so that patients and families are made aware of the results of studies and their correct interpretation. There will be no charge for Harvoni, the physician services, or laboratory tests done as part of this study.

4.5 Data Elements

The following laboratory tests and procedures will be used as the primary data elements:

- Medical history
- Physical examination

- Photographs of areas with PCT skin lesions
- Spot plasma and urinary porphyrins (including HPLC), and urinary creatinine concentrations
- Alcohol Consumption Questionnaire will assess alcohol use
- Serum HCV RNA by PCR
- Anti-HCV antibodies
- Complete metabolic panel (CMP), which includes:
 - Liver chemistries (serum ALT, AST, total bilirubin, albumin, total protein)
 - Serum creatinine, sodium, potassium, chloride, carbon dioxide, calcium, BUN, glucose
- CBC with differential
- INR
- Serum iron and TIBC
- Serum ferritin

These will be completed per the 4.7 Schedule of Events Flow Chart. In addition there will be adverse events reviewed at each visit.

If liver biopsies and/or Fibroscans have been performed, as part of standard of care, results of these will be entered into the study data CRF's; however, no liver biopsies or Fibroscans will be required for inclusion.

4.6 Study Procedures

Screening and Enrollment:

Potential subjects will be invited to take part and to sign informed consent forms. All participating centers will obtain CIRB approval.

Data collected at baseline will include demographic and clinical information. The screening laboratory tests will be:

- Serum HCV RNA by PCR (obtained within 30 days of enrollment)
- Anti-HCV antibodies
- CMP
- CBC with differential
- INR (if not done within 4 months of screening date)
- PTT
- Hepatitis B surface antigen
- Hemoglobin (Hgb) A1c
- Antibodies to HIV (if not done within 4 months of screening date). Those found positive will undergo HIV RNA and CD4 counts, to assure immune competence. Subjects with known HIV infection, with CD4 counts > 350/ μ L, whether receiving anti-HIV therapy or not, will **not** be excluded unless they require continuation of drug(s) contraindicated in subjects to receive Harvoni

- Spot plasma total porphyrins
- Spot urine delta-aminolevulinic acid (ALA), porphobilinogen (PBG), total porphyrins (including HPLC), and creatinine concentrations
- UROD enzyme activity and mutation analysis, if not previously done
- Serum iron and TIBC
- Serum Ferritin
- *HFE* genetic testing for C282Y and H63D, if not previously done
- Documentation of PCT symptoms and photographs of affected regions (hands, forearms, etc.)
- Alcohol and Tobacco use questionnaires
- Urine pregnancy for females of child-bearing potential

At baseline/screening, following informed consent, a standard interview to assess history of past and current alcohol use. HCV genotype should be confirmed prior to the screening visit as standard of care. History of smoking and current smoking status will also be assessed by interview and results recorded in suitable case report forms (CRFs). All prescription or over-the-counter drugs, including herbals, botanicals, and 'supplements' currently being taken or taken within the two weeks prior to screening, will be recorded, to include name, daily dose, and approximate duration of therapy (estimated to nearest month and year). Particular inquiry will be made regarding any and all estrogen use, including phyto-estrogens, as may be found in herbals and dietary supplements, such as black cohosh. All subjects will be evaluated by a hepatologist (the site PI or a Co-I) at baseline for liver disease based on the criteria detailed above for inclusion/exclusion.

The investigator will review that the subject has the typical clinical features of PCT, specifically blistering cutaneous photosensitivity, milia, thickened sclerodermatous changes, and/or skin fragility. The diagnosis of PCT will be confirmed at screening from the urine and plasma total porphyrin results. The urinary total porphyrin excretion should be >800 mcg/g creatinine and the HPLC pattern typical of PCT, with a predominance of uro- and heptacarboxyl- porphyrins. The plasma porphyrin results should be >2.7 μ g/dL with a predominance of uro- and heptacarboxyl- porphyrins, and a fluorescence emission peak at ~ 619 nm (with excitation at ~ 410 nm).

At baseline, subjects who, within the prior 120 days, have not already had either hepatic elastography with Fibroscan or similar technique and/or had Fibrosure-HCV testing performed will undergo one of these measures. The decision of which test to perform will be at the discretion of the site PI's (similar testing will again be performed at the end of the study, as shown in the Schedule of Events).

All subjects found to be eligible will be invited to take part in the study. We anticipate that most subjects at baseline will not be undergoing treatment for PCT or CHC, but they may have done so in the past and have recurrence of active PCT with persistent or recurrent CHC. To be eligible, subjects previously treated for CHC must have ended such treatment at least 30 days prior to enrollment into this study.

Treatment and Follow-up Visits:

The therapy will be Harvoni at the usual dose (90 mg of ledipasvir and 400 mg of sofosbuvir) and duration for CHC therapy. One tablet taken daily for 8 weeks for patients without cirrhosis, not previously treated with HCV GT1 and HCV RNA < 6 million IU/mL; 12 or 24 weeks, duration to be determined based upon clinical features and prior treatment experience. 8 or 12 weeks for subjects with or without cirrhosis, not previously treated with anti-virals for CHC, and 24 weeks for subjects with cirrhosis who were previously treated with anti-virals for CHC without having achieved SVR. During the first year study visits will be monthly, and this includes the treatment period of either 12 or 24 weeks. To assess cure of HCV infection, repeated HCV RNA levels at 3, 6, and 12 months after end of Harvoni therapy will be done, as well as annually thereafter. Evaluation by a hepatologist at follow up visits will be as needed, determined by the screening lab test results and by clinical and lab findings at follow-up visits.

Lab measures to be checked monthly during therapy will include CBC, CMP, plasma total porphyrins, urinary total porphyrins (with HPLC), and levels of HCV RNA in serum by quantitative PCR (Section 4.7 Schedule of Events).

Porphyrin specific lab tests will be performed at the UTMB Porphyria Laboratory; all other labs will be performed at Covance Laboratories.

Subjects who have their treatment discontinued for any reason will continue to be followed until the end of the study, including longer-term follow up visits, unless they withdraw consent. If a subject becomes pregnant during the study Harvoni will be discontinued. The outcome of the pregnancy will not be followed as part of this study. Pregnancy during the study should be reported as an SAE.

Longer-Term Follow-up:

12 months after beginning treatment, subjects will be asked to return every four months for one year, with repeat of interval history and physical examination (especially to reassess the status of cutaneous lesions of PCT) and the above studies.

Every effort will be made to have all subjects return annually thereafter as part of the Longitudinal Study of the Porphyrias, for at least 5 years, to assess whether there has been relapse either of active PCT or HCV infection. This will be done by assessing history of skin symptoms and measuring plasma and urine porphyrins. All subjects will be strongly encouraged to return to a study center if they think they are experiencing recurrence of active PCT. If there has been relapse, subjects will be treated further as part of routine standard of care, and their clinical and biochemical features will continue to be recorded.

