4.7 Schedule of Events

	Screening (-30 to -1 Days)	Day 0	Day 30	Day 60	Day 90	Day 120	Day 150	Day 180	Day 210	Day 240	Day 270	Day 300	Day 330	Day 360	Day 480	Day 600	Day 720
			(Window +/- 7 days)														
			M1	M2	M3	M4	M5	M6	M7	M8	M9	M10	M11	M12	M16	M20	M24
Consent	X																
Complete Medical History	X																
Interval Medical History		X	X	X	X	X	X	X	X	X	X	X	X	X	X	X	X
Physical Examination	X	X			X			X			X			X	X	X	X
Skin Assessment (including pictures)	X	X	X	X	X	X	X	X	X	X	X	X	X	X	X	X	X
Alcohol & Tobacco use questionnaires	X																
Adverse Event/SAE Review														Each visit			
Urine Pregnancy	X																
Anti-HCV antibodies	X																
PTT	X																
Hepatitis B Surface Antigen	X																
HIV-1/HIV-2 Antibodies	X																
Serum Ferritin	X																
Serum iron and TIBC	X																
Complete Metabolic Panel\$	X	X	X	X	X	X	X	X	X	X	X	X	X	X	X	X	X
INR**	X																
HbA1c	X																
Erythrocyte UROD enzyme activity*	X																
UROD mutation analysis*	X																
HFE genetic testing*	X																
Hematology with Differential#	X	X	X	X	X	[X]*	[X]*	X	X	X	X	X	X	X	X	X	X
HCV RNA	X	X				[X]*	[X]*	[X]									
Plasma Total Porphyrins	X	X	X	X	X	X	X	X	X	X	X	X	X	X	X	X	X
Spot Urine ALA, PBG, Total Porphyrins	X	X	X	X	X	X	X	X	X	X	X	X	X	X	X	X	X
Fibroscan (if available at institution)	X														X		X
Dispense Study Drug [€]		X	X	X	X	X	X	X	X								

Hematology (complete blood count): white blood cell count (WBC), red blood cell count (RBC), hemoglobin, hematocrit, platelet count

\$Comprehensive metabolic panel: sodium, potassium, chloride, carbon dioxide, calcium, BUN, creatinine, glucose, and liver panel, including total protein, albumin, total bilirubin (TBR), alanine aminotransferase (ALT), aspartate aminotransferase (AST), alkaline phosphatase (AP)

*If not previously done

**INR (if not done within 4 months of screening)

[€]Drug is only to be dispensed at months 2-6 if additional therapy is warranted

[X]* Samples at these time points will be obtained only in subjects with cirrhosis who 24 weeks of Harvoni therapy is indicated; [X] Samples at these time points will be obtained 3, 6, and 12 months after the end of Harvoni treatment, and annually till end of study or EOT

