4.8 Investigational Product

All study drug will be stored and dispensed from individual centers' research pharmacies according to their standard operating procedures. Drug will only be dispensed after authorized by a site Investigator and to a member of the study team. All study drug will be provided to each site by Gilead Sciences, Inc. through communication with Wake Forest University School of Medicine.

Obtaining Study Drug: Once a potential participant is identified, the site will contact the project manager at Wake Forest University School of Medicine to have study drug sent to the research pharmacy at the site to be dispensed to the study team and the patient.

Dispensing, Dosage, and Accountability: All participants will receive treatment for either 8, 12, or 24 weeks depending upon the usual clinical criteria and recommendations that inform clinical treatment of HCV with Harvoni: We anticipate that, for most subjects, the duration of indicated treatment will be 12 weeks. For patients with cirrhosis, previously treated for HCV infection without response or with response followed by relapse, the duration of treatment will be 24 weeks. Study drug will be dispensed with 4 week supplies (28 tablets). It is recommended that 1 week of additional drug is provided, in case of the need for follow-up appointments to be rescheduled. New supplies of drug will not be provided to subjects until the previous supply has been accounted for by the site coordinator or investigational pharmacy and reconciled. Medication will only be provided at in person study visits, no medication will be mailed to subjects.

The dosage is one tablet of the combination of ledipasvir (90 mg) + sofosbuvir (400 mg) taken daily with or without food. Tablets should not be broken or chewed. No dose adjustments are recommended based upon considerations of age, mild or moderate renal impairment, or mild, moderate, or severe hepatic impairment.

At each study visit the participant will bring all study drug with him or her. The site coordinator will count and reconcile all study medication at each visit. At each visit the subject will return all previous study drug and empty bottles and receive a new 4 week supply. At the final treatment visit (8, 12, or 24 weeks, as may be appropriate), a new supply will not be issued.

Study Drug Destruction: Medication returned by subjects can be destroyed onsite per institutional SOP.

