Complete Biochemical remission of PCT: Complete biochemical remission of PCT will be measured as a decrease of the sum of urinary uro- and hepta-carboxyl porphyrins to less than 100 mcg/g creatinine, and a normal urine porphyrin HPLC pattern, defined as the total of highly carboxylated porphyrins (uro- and heptacarboxyl-porphyrins) being less than that of coproporphyrins, and absence of a fluorescence peak by fluorescence scanning. The proportion of patients who achieve complete biochemical remission by the end of study period will be computed and the median time to resolution by this definition will be computed using Kaplan-Meier estimation. Because of underlying liver disease and/or possible continuing alcohol use, total urinary porphyrins may remain elevated, due to increased coproporphyrins. We will explore whether and to what extent total urinary porphyrins may remain elevated, due to increased coproporphyrins descriptively in these subjects.

Cure of CHC: Cure of CHC will be defined as no detectable HCV RNA at end of treatment (EOT) and persisting for at least 12 weeks after EOT, now taken as usual definition of sustained virological response (SVR). The proportion of patients who achieve CHC cure will be reported.

Sample Size: The primary study hypothesis is that the proportion of patients whose PCT resolves by 7 months will be non-inferior to the performance goal of 50%. This performance goal is based on previously published data that reported a median time to resolution between 6-7 months for PCT patients undergoing treatment with iron reduction by therapeutic phlebotomies or hydroxychloroquine (Singal et al, 2012). The non-inferiority margin will be set to 10%; a difference from the performance goal judged to be both clinically acceptable and well within the margin needed to assure that the performance of Harvoni is at established levels of benefit from conventional therapies. Thus, the null hypothesis tested by this study is $H_0: \pi \leq 0.40$, against the alternative hypothesis $H_1: \pi > 0.40$.

Sample size requirements are based on an exact test of a binomial proportion. Assuming that the study drug has a true success probability of 58%, 49 subjects yield 80% power to reject the null hypothesis at a one-sided significance level of 0.05.

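### The HCV RNA row in the Schedule of Events does not carry the sampling set out in Section 4.6; on the grid, 8- and 12-week patients have no end-of-treatment draw

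*Combined protocol and SAP*

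**What the plan says.** **Text.** Section 4.6 (Treatment and Follow-up Visits) states: "Lab measures to be checked monthly during therapy will include CBC, CMP, plasma total porphyrins". The same list ends with "levels of HCV RNA in serum by quantitative PCR (Section 4.7 Schedule of Events", so the schedule is named as the place where this sampling is set out. After treatment, "repeated HCV RNA levels at 3, 6, and 12 months after end of Harvoni therapy will be done, as well as annually thereafter". Neither sentence is limited by course length.

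**Course lengths.** Section 4.8: "All participants will receive treatment for either 8, 12, or 24 weeks". It anticipates 12 weeks for most patients. Section 4.6 says of the monthly first-year visits that "this includes the treatment period of either 12 or 24 weeks", which leaves out the 8-week course.

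**Grid.** The HCV RNA row in Section 4.7, as it reads after extraction from the PDF, has X at Screening and Day 0, blanks at Days 30, 60 and 90, `[X]*` at Days 120 and 150, `[X]` at Day 180, and blanks from Day 210 to Day 720. The `[X]*` footnote reads: "Samples at these time points will be obtained only in subjects with cirrhosis who 24 weeks of Harvoni therapy is indicated". The `[X]` footnote reads: "Samples at these time points will be obtained 3, 6, and 12 months after the end of Harvoni treatment", with annual samples after that.

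**Endpoint.** Section 6 (Cure of CHC) defines cure as "no detectable HCV RNA at end of treatment (EOT) and persisting for at least 12 weeks after EOT" and reports it as a proportion.

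**The concern.** The text and the grid give sites different instructions. A coordinator working from the schedule, as is usual, would draw no HCV RNA between Day 0 and Day 180 in a patient on 8 or 12 weeks. The first half of the cure definition, an undetectable result at EOT, would then be unobserved in those patients. The missing-data rules in Section 6 are written for the primary endpoint. Nothing says whether a patient with an undetectable later sample but no EOT value counts as cured. The choice would be made after the fact, or would differ with each site's practice. Section 4 also intends to set the cure rate beside published results, which needs a consistently measured endpoint.

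**Working it through.** The plan gives no figure for this point, so the check compares sampling days with the visit grid.

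**Inputs.** Course lengths of 8, 12 and 24 weeks (Section 4.8). Visit days, the ±7-day window and the HCV RNA marks (Section 4.7). Day 0 is taken as the first dose, since drug is dispensed then. Three months is taken as 3 × 30.4 ≈ 91 days.

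**Formulas.** EOT = 7 × weeks. Twelve-week point = EOT + 84. Three-month point = EOT + 91. Weeks after EOT at day d = (d − EOT)/7.

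**Step 1: the EOT draw.**

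| Course | EOT | Visit window holding EOT | HCV RNA mark |
|---|---|---|---|
| 8 weeks | 7 × 8 = Day 56 | Day 60 (53–67) | none |
| 12 weeks | 7 × 12 = Day 84 | Day 90 (83–97) | none |
| 24 weeks | 7 × 24 = Day 168 | none (Day 150 window ends at 157; Day 180 window starts at 173) | – |

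No section names an EOT draw. The text implies one for the shorter courses if the Day 60 and Day 90 visits are read as the last monthly on-treatment checks, although nominally they fall 4 and 6 days after EOT.

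**Step 2: the post-treatment draw.**

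| Course | EOT + 84 | EOT + 91 | Nearest visit to 3 months | Mark there |
|---|---|---|---|---|
| 8 weeks | Day 140 | Day 147 | Day 150 | `[X]*`, 24-week patients only |
| 12 weeks | Day 168 | Day 175 | Day 180 | `[X]` |
| 24 weeks | Day 252 | Day 259 | Day 270 | none |

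**Step 3: what the Day 180 sample (window 173–187) delivers.**

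- 8 weeks: (173 − 56)/7 = 16.7 to (187 − 56)/7 = 18.7 weeks after EOT. Meets at least 12 weeks.
- 12 weeks: (173 − 84)/7 = 12.7 to (187 − 84)/7 = 14.7 weeks. Meets it.
- 24 weeks: (173 − 168)/7 = 0.7 to (187 − 168)/7 = 2.7 weeks. Does not meet it, and no later cell is marked. That draw rests on Section 4.6 and the `[X]` footnote alone.

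**Step 4: can the row be trusted?** It has 17 cells, matching the header. Its `[X]*` marks stand in the same columns as those of the hematology row. The Physical Examination row shows that the extraction kept interior blanks in place. A column shift is therefore unlikely, but this does not prove that no marks were lost.

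**The case against.** The strongest reply is that the missing EOT draw depends on blank cells in an extracted table. In that table, the adverse-event entry covering all visits and the window note each sit in a single column, so spanning entries were collapsed. The `[X]` footnote speaks of several time points, yet only one `[X]` cell survives. The hematology row has X at Days 30 to 90, and Section 4.6 lists CBC and HCV RNA together as monthly. Lost marks are possible, so the original table has to be checked first.

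The `[X]*` restriction also agrees with the text for on-treatment draws, because by Days 120 and 150 only 24-week patients are still on therapy. It causes trouble only because Day 150 is also the visit nearest to 3 months after an 8-week course.

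Two stronger readings are tempting, and neither is supported.

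- A reader might infer that 8-week patients have no qualifying post-treatment sample. Section 4.6 and the `[X]` footnote require one at 3 months for every course, and the marked Day 180 sample is already more than 12 weeks after their EOT.
- A reader might infer that cure could not be ascertained. A site following Section 4.6 would obtain on-treatment samples up to about EOT and a 3-month sample.

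The objection does not remove the conflict in instructions. On the grid as it reads, the Day 60 and Day 90 draws are absent, Day 150 is closed to 8-week patients, and the single `[X]` cell fits 3 months after a 12-week course only.

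**Conclusion.** The point holds as an inconsistency between Sections 4.6 and 4.7 that puts part of a secondary endpoint at risk. If every site follows the text, no EOT value need be lost. If every site follows the grid, all 8- and 12-week patients lack one. Should the expectation in Section 4.8 hold, the 12-week patients alone would be more than half of 49, that is, at least 25. The documents do not give the mix of course lengths or say which instruction sites use, so nothing narrower can be stated.

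This rests on the row having survived extraction and on Day 0 being the first dose. Cure of CHC is reported descriptively. The primary analysis uses plasma porphyrins, which are marked at every visit, so the rule of 26 or more successes in 49, the power and the error rate are unaffected. The correction should be made, but it does not threaten the trial's main conclusion.

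**What to change.** First check the original Section 4.7 table for marks lost in extraction. Then reconcile the HCV RNA row and its footnotes with Section 4.6:

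- mark the monthly on-treatment draws;
- add an explicit EOT draw for each course length (8, 12 and 24 weeks), with a window that contains Day 56, 84 or 168;
- mark the 3-, 6- and 12-month draws as counted from each patient's own EOT;
- limit the 24-week-only footnote to on-treatment draws, so that it no longer closes Day 150 to 8-week patients;
- reconcile the Section 4.6 sentence that names only two treatment periods with the three in Section 4.8.

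The cost is a schedule correction. Section 4.6 already commits to the monthly and post-treatment assays, and blood is already drawn at these visits. The one possible addition is an EOT draw for 24-week patients, since no visit window contains Day 168; Section 4.8 already refers to a final treatment visit at 24 weeks. The sample size and the analysis do not change.
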